Appendix H: Major Bleed classification/definition

***Bleeding**

Classified as Type 0 – 5 according to the following BARC definitions³⁶:

Type 0: No bleeding

Type 1: Bleeding that is not actionable and does not cause the patient to seek unscheduled performance of studies, hospitalization, or treatment by a healthcare professional; may include episodes leading to self-discontinuation of medical therapy by the patient without consulting a healthcare professional

Type 2 (minor): Any overt, actionable sign of hemorrhage (e.g. more bleeding than would be expected for a clinical circumstance, including bleeding found by imaging alone) that does not fit the criteria for Type 3, 4, or 5 but does meet at least one of the following criteria: (1) requiring nonsurgical, medical intervention by a healthcare professional, (2) leading to hospitalization or increased level of care, or (3) prompting evaluation

Type 3 (major):

Type 3a:

- Any transfusion with overt bleeding
- Overt bleeding plus a hemoglobin drop of ≥ 3 to < 5 g/dL (provided hemoglobin drop is related to bleeding)

Type 3b:

- Overt bleeding plus hemoglobin drop ≥ 5 g/dL (provided hemoglobin drop is related to bleed)
- Cardiac tamponade
- Bleeding requiring surgical intervention for control (excluding dental/nasal/skin/hemorrhoid)
- Bleeding requiring intravenous vasoactive drugs

Type 3c:

- Intracranial hemorrhage including subdural hemorrhages (does not include microbleeds or hemorrhagic transformation, does include intraspinal)
- Subcategories confirmed by autopsy or imaging or lumbar puncture
- Intraocular bleed compromising vision

Type 4: Coronary artery bypass graft (CABG)–related bleeding:

- Perioperative intracranial bleeding within 48 hours
- Reoperation after closure of sternotomy for the purpose of controlling bleeding
- Transfusion of ≥ 5 units whole blood or packed red blood cells within a 48-hour period (only allogenic transfusions are considered transfusions for CABG-related bleeds)
- Chest tube output ≥ 2 L within a 24-hour period

Notes: If a CABG-related bleed is not adjudicated as at least a type 3 severity event, it will not be classified as a bleeding event. If a bleeding event occurs with a clear temporal relationship to CABG (i.e. within a 48-hour timeframe) but does not meet type 4 severity criteria, it will not be classified as a bleeding event.

Type 5: Fatal bleeding

Fatal bleeding is bleeding that directly causes death with no other explainable cause.

BARC fatal bleeding is categorized as either definite or probable as follows:

Type 5a:

Probably fatal bleeding: bleeding that is clinically suspicious as the cause of death, but the bleeding is not directly observed and there is no autopsy or confirmatory imaging

Type 5b:

Definite fatal bleeding: bleeding that is directly observed (by either clinical specimen [blood, emesis, stool, etc.] or imaging) or confirmed on autopsy

The site of fatal bleeding is specified as intracranial, gastrointestinal, retroperitoneal, pulmonary, pericardial, genitourinary, or other.

Bleeding Academic Research Consortium (BARC) indicates fatal bleeding is meant to capture deaths that are directly due to bleeding with no other cause. The time interval from the bleeding event to the death should be considered with respect to likely causality, but there is no specific time limit proposed. Bleeding that is contributory but not directly causal to death is not classified as fatal bleeding but may be categorized as other forms of bleeding. Bleeding that leads to cessation of antithrombotic or other therapies may be contributory but again would not be classified as fatal bleeding.

Appendix I: Cardiovascular Mortality Definition

Cardiovascular Mortality	
▪ Death resulting from an acute myocardial infarction (MI), sudden cardiac death, death due to heart failure (HF), death due to stroke, death due to cardiovascular (CV) procedures, death due to CV hemorrhage, and death due to other CV causes.
--------------------------	----------------------------------------------------------------------------------------------------------------------------------------------------------------------------------------------------------------------------------------------------------------------------------------------------

Appendix J: Definitions of Potential Adverse Event

- **Air Embolus** – symptomatic event resulting from the introduction of air into the circulatory system
- **Allergic reaction** – idiosyncratic reaction to the device implanted or to nickel
- **Anesthesia reaction** – undesired reaction to anesthetic agent
- **Arrhythmia** – cardiac rhythm disturbance
- **Bleeding** –see **Appendix I**
- **Cardiac arrest** – failure of the heart to contract
- **Cardiac tamponade** – constriction of the heart causing inefficient contraction resulting from accumulation of excess fluid in the pericardium
- **Death** – permanent cessation of all vital bodily functions
- **Device embolization** – movement of the device from its intended location
- **Device migration** – movement of the device within its intended location
- **Embolic event** – acute vascular insufficiency or occlusion of the extremities or any non-central nervous system organ associated with clinical, imaging, surgical/autopsy evidence of arterial occlusion in the absence of other likely mechanism (e.g., trauma, atherosclerosis, or instrumentation). When there is presence of prior peripheral artery disease, angiographic or surgical or autopsy evidence is required to show abrupt arterial occlusion
- **Fever** – defined as a body temperature > 37.5 or 38.3 °C (99.5 or 100.9 °F)
- **Foreign body embolization** – movement of device material, delivery system material, or other material from its intended location
- **Hypotension** – sustained systolic blood pressure < 90 mmHg
- **Hypertension** – systolic blood pressure of > 160 mmHg
- **Infection** – invasion and growth of a pathogenic organism within the body
- **Multi-Organ Failure** – the failure of two or more systems, such as the cardiovascular and renal systems, and is a common consequence of sepsis (the presence of bacteria in the blood) and of shock (very low blood pressure)
- **Myocardial infarction (heart attack)** – the death of heart muscle from the sudden blockage of a coronary artery by a blood clot
- **Perforation** – physical penetration of a vessel or the myocardium
- **Pericardial effusion** – abnormal fluid collection around the heart without hemodynamic compromise
- **Renal failure/dysfunction** – inability of kidneys to perform normal functions
- **Respiratory failure** – inability of the lungs to perform normal functions
- **Seizure** – uncontrolled electrical activity in the brain, which may produce a physical convulsion, minor physical signs, thought disturbances, or a combination of symptoms
- **Significant Residual Flow** – flow > 3 mm jet into the LAA
- **Stroke** – an acute episode (lasting > 24 hours) of focal or global neurological dysfunction caused by brain, spinal cord, or retinal vascular injury as a result of hemorrhage or infarction. Strokes are characterized as follows³⁵:
 - **Ischemic Stroke**: an acute episode of focal cerebral, spinal, or retinal dysfunction caused by infarction of the central nervous system tissue. Hemorrhage may be a consequence of ischemic stroke. In this situation, the stroke is an ischemic stroke with hemorrhagic transformation and not a hemorrhagic stroke.

Clinical Investigation Plan

- **Hemorrhagic Stroke**: an acute episode of focal or global cerebral or spinal dysfunction caused by intraparenchymal, intraventricular, or subarachnoid hemorrhage
- **Undetermined Stroke**: an acute episode of focal or global neurological dysfunction caused by presumed brain, spinal cord, or retinal vascular injury as a result of hemorrhage or infarction but with insufficient information to allow categorization as ischemic or hemorrhagic stroke
- **Thrombus Formation** – a blood clot
- **Transient Ischemic Attack (TIA)**– a transient episode (lasting \leq 24 hours) of focal neurological dysfunction caused by brain, spinal cord, or retinal ischemia, *without* acute infarction on brain imaging
- **Valvular regurgitation/insufficiency** – backflow of blood during contraction of the heart; caused by a defective heart valve
- **Vascular access site injury** – damage at vascular access site (e.g., AV fistula, hematoma, and aneurysm)
- **Vessel Trauma/Injury** – traumatic injuries that damage an artery or vein

The study is a post-approval study to compile real world outcome data on the use of the Amplatzer Cardiac Plug (“ACP”) and the next generation Amplatzer Amulet left atrial appendage occluder (“Amulet”) upon its approval by Health Canada, in subjects with non-valvular atrial fibrillation who are at increased risk for stroke and systemic embolism. [REDACTED]

1.3 **Clinical Investigation Design**

The Amplatzer family of left atrial appendage (“LAA”) occluder devices (ACP and Amulet) will be clinically evaluated through this post-approval study. This is a prospective, multicenter, non-randomized, observational, post-approval study on subjects who will undergo the implant of an Amplatzer LAA occluder.

1.4 **Endpoints**

As the coronavirus disease 2019 (COVID-19) has spread around the world, Abbott has taken steps to minimize the potential confounding effect of the disease. In alignment with the guidance documents “FDA Guidance on Conduct of Clinical Trials of Medical Products during the COVID-19 Public Health Emergency,” updated 03JUN2020, “Statistical Considerations for Clinical Trials During the COVID-19 Public Health Emergency,” dated June 2020, and EU “Guidance on the Management of Clinical Trials During the COVID-19 (Coronavirus) Pandemic,” updated 28APR2020, additional consideration was given to the impact of COVID-19 on the primary and secondary endpoint analysis. [REDACTED]

1.4.1 **Primary Safety Endpoint**

The primary safety endpoint is the occurrence of one of the following events between the time of implant and 7 days post-procedure or hospital discharge (whichever is later): all cause death, ischemic stroke, systemic embolism, or device- or procedure-related events requiring open cardiac surgery or major endovascular repair.

Percutaneous catheter drainage of pericardial effusion, snaring of an embolized device, thrombin injection to treat femoral pseudoaneurysm, and nonsurgical treatments of access site complications will not be included in the assessment of the primary safety endpoint.

1.4.2 **Primary Efficacy Endpoints**

Primary effectiveness endpoint 1 is the occurrence of stroke (including ischemic or hemorrhagic), systemic embolism, cardiovascular death, or unexplained death through 24 months.

Primary effectiveness endpoint 2 is the occurrence of ischemic stroke or systemic embolism through 24 months.

1.4.3 Secondary Endpoint

The secondary endpoint is a comparison of the observed rate of ischemic stroke or systemic embolism at 24 months with the CHA₂DS₂-VASc predicted rate.

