Primary Endpoints	
This study has three primary endpoints:
 
 • Efficacy Endpoint 1: The occurrence of the composite of stroke (including ischemic or hemorrhagic), systemic embolism, or cardiovascular or unexplained death at 24 months from the time of enrollment • Efficacy Endpoint 2: The occurrence of ischemic stroke or systemic embolism at 24 months from the time of enrollment • Safety Endpoint: The occurrence of one of the following events between the time of implant and within 7 days of the procedure or by hospital discharge, whichever is later: all-cause death, ischemic stroke, systemic embolism, or device or procedure-related events requiring open cardiac surgery or major endovascular repair
Secondary Endpoint	Comparison of the observed rate of ischemic stroke at 24months with the CHA ₂ DS ₂ -VASc predicted rate.
Descriptive Endpoints/Outcomes Measures	
The following endpoints will be summarized descriptively:
 
 • Oral anticoagulant use over time • Device closure at the 2 month visit

	
 • Procedural success • Technical success • Procedure duration • Device thrombosis • Transient ischemic attack • Death • Major bleeding
Enrollment Criteria	
Prospective Enrollments Patients in whom an AMPLATZER LAA Occluder device is intended to be implanted
 
Retrospective Enrollments Patients who underwent an AMPLATZER LAA Occluder implant attempt after the device was approved in the applicable geography

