4.2.3 Enrollment period and study duration

4.3 Endpoints

4.3.1 Primary endpoints

This study has three primary endpoints:

1. Efficacy Endpoint 1: The occurrence of the composite of stroke (including ischemic or hemorrhagic), systemic embolism and cardiovascular or unexplained death at 24 months
2. Efficacy Endpoint 2: The occurrence of ischemic stroke or systemic embolism at 24 months
3. Safety Endpoint: The occurrence of one of the following events between the time of implant and within 7 days of the procedure or by hospital discharge, whichever is later: all cause death, ischemic stroke, systemic embolism, or device or procedure-related events requiring open cardiac surgery or major endovascular repair*

* NOTE: Percutaneous catheter drainage of pericardial effusion, snaring of an embolized device, thrombin injection to treat femoral pseudoaneurysm and nonsurgical treatments of access site complications will not be included in the assessment of the third primary endpoint.

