4.3.2 Secondary endpoint

The secondary endpoint is a comparison of the observed rate of ischemic stroke at 24 months with the CHA₂DS₂-VASc predicted rate.

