14.1 Primary Endpoints

There are three primary endpoints, two effectiveness endpoints and one safety endpoint.

14.1.1 Primary Effectiveness Endpoint 1:

Primary effectiveness endpoint 1 is the occurrence of the composite of stroke (including ischemic or hemorrhagic), systemic embolism, or cardiovascular or unexplained death at 24 months.

Hypothesis:

Ho: $\lambda_1 \geq 9.6\%$

Ha: $\lambda_1 < 9.6\%$,
where λ_1 is the rate of primary composite endpoint 1 at 24 months.

Analysis Methods:

Kaplan-Meier analysis will be used to estimate the event rate of at 24 months (731 days post implant). The 97.5% upper confidence bound for the event rate must be less than 9.6% in order to declare success. [REDACTED]

Analysis Population:

Subjects in this study who receive an implant of the AMPLATZER LAA Occluder will be included in the analysis.

14.1.2 Primary Effectiveness Endpoint 2:

Primary effectiveness endpoint 2 is the occurrence of the composite of ischemic stroke or systemic embolism at 24 months.

Hypothesis:

Ho: $\lambda_2 \geq 6.6\%$

Ha: $\lambda_2 < 6.6\%$,

where λ_2 is the rate of primary composite endpoint 2 at 24 months.

Analysis Methods:

Kaplan-Meier analysis will be used to estimate the rate of event at 24 months (731 days post implant). The 97.5% upper confidence bound for the event rate must be less than 6.6% in order to declare success. [REDACTED]

Analysis Population:

Subjects in this study who receive an implant of the AMPLATZER LAA Occluder will be included in the analysis.

14.1.3 Primary Safety Endpoint:

The primary safety endpoint is the occurrence of one of the following events between the time of implant and within 7 days of the procedure or by hospital discharge, whichever is later: All-cause death, ischemic stroke, systemic embolism, or device or procedure related events requiring open cardiac surgery or major endovascular repair (percutaneous catheter drainage of pericardial effusion, snaring of an embolized device, thrombin injection to treat femoral pseudoaneurysm, and nonsurgical treatments of access site complication will not be included in the assessment of the third primary endpoint).

Hypothesis:

Ho: $P \geq 2.66\%$

Ha: $P < 2.66\%$,

where P is the proportion of subjects experiencing a primary safety event within 7 days of the procedure or by hospital discharge, whichever is later.

Analysis Methods:

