14.2.2 Analysis population

The analysis will include subjects who receive an implant of an AMPLATZER LAA Occluder.

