2.3.1.1 Primary Safety Endpoint

The primary safety endpoint will be assessed in the attempt population. The hypothesis is formally stated:

$$H_0: P \geq 2.66\%$$

$$H_a: P < 2.66\%$$

where P is the proportion of subjects who experience a primary safety endpoint event. P will be estimated by the 97.5% upper confidence bound (UCB) of the event rate [REDACTED]

2.3.1.2 Primary Effectiveness Endpoint 1

Primary effectiveness endpoint 1 will be assessed in the implant population. The hypothesis is formally stated:

$$H_0: \lambda_1 \geq 9.6\%$$

$$H_a: \lambda_1 < 9.6\%$$

where λ_1 is the endpoint event rate. λ_1 will be estimated by the 97.5% UCB of the Kaplan-Meier event rate.

2.3.1.3 Primary Effectiveness Endpoint 2

Primary effectiveness endpoint 2 will be assessed in the implant population. The hypothesis is formally stated:

$$H_0: \lambda_2 \geq 6.6\%$$

$$H_a: \lambda_2 < 6.6\%$$

where λ_2 is the endpoint event rate. λ_2 will be estimated by the 97.5% UCB of the Kaplan-Meier event rate.

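### The secondary endpoint counts ischemic stroke in the protocol but ischemic stroke or systemic embolism in the SAP, and under the SAP wording no visible endpoint gives the 24-month rate of ischemic stroke alone

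*SAP*

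**What the plan says.** The protocol gives the secondary endpoint in three places, each time with ischemic stroke alone as the observed event:

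- Synopsis: "Comparison of the observed rate of ischemic stroke at 24months with the" CHA₂DS₂-VASc prediction.
- Section 4.3.2: "The secondary endpoint is a comparison of the observed rate of ischemic stroke at 24 months", set against the same prediction.
- Section 14.2: the same sentence again.

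SAP 1.4.3 gives it as a "comparison of the observed rate of ischemic stroke or systemic embolism at 24 months", also against the CHA₂DS₂-VASc prediction.

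The wider event already belongs to a primary endpoint. Protocol 4.3.1 lists efficacy endpoint 2 as "The occurrence of ischemic stroke or systemic embolism at 24 months", and SAP 1.4.2 agrees: "Primary effectiveness endpoint 2 is the occurrence of ischemic stroke or systemic embolism through 24 months". That endpoint is tested against a fixed goal (protocol 14.1.2): "The 97.5% upper confidence bound for the event rate must be less than 6.6% in order to declare success".

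As far as can be seen, both endpoints use implanted subjects. Protocol 14.2.2 says of the secondary endpoint: "The analysis will include subjects who receive an implant of an AMPLATZER LAA Occluder". SAP 2.3.1.3 says: "Primary effectiveness endpoint 2 will be assessed in the implant population".

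The analysis method for the secondary endpoint, and with it the source of the predicted rate, is redacted in both documents (protocol 14.2.1, SAP 2.3.2).

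**The concern.** Comparing an observed rate with a predicted one makes sense only if both sides count the same event. With two definitions in force, an analyst who follows the SAP can report a secondary result that is not the one the protocol names.

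There is also a loss of information. In the protocol, the secondary endpoint is the only one that isolates ischemic stroke. If it becomes the composite, its event and horizon are those of primary effectiveness endpoint 2, and only the comparator differs. This is a device meant to prevent embolization of thrombus from the appendage, so a 24-month rate of ischemic stroke alone is a figure readers will expect to find.

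**Working it through.** The plan states no rate, power or sample size for this endpoint that could be reproduced, so the check is mainly textual.

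**Step 1. The definitions side by side.**

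| Place | Observed event | Horizon | Comparator |
|---|---|---|---|
| Protocol Synopsis | ischemic stroke | 24 months | CHA₂DS₂-VASc prediction |
| Protocol 4.3.2 | ischemic stroke | 24 months | CHA₂DS₂-VASc prediction |
| Protocol 14.2 | ischemic stroke | 24 months | CHA₂DS₂-VASc prediction |
| SAP 1.4.3 | ischemic stroke or systemic embolism | 24 months | CHA₂DS₂-VASc prediction |
| Primary effectiveness endpoint 2 (both documents) | ischemic stroke or systemic embolism | 24 months | fixed goal, 6.6% |

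All three protocol statements agree with each other, and the one visible SAP statement differs from them. All are complete sentences in current text. The protocol itself treats the two events as distinct, since it uses one for primary endpoint 2 and the other for the secondary endpoint.

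**Step 2. Does any other visible SAP endpoint give ischemic stroke alone at 24 months?** The SAP shows 3 primary + 1 secondary + 9 descriptive = 13 endpoints.

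- Primary effectiveness 1: a composite of all stroke, systemic embolism, and cardiovascular or unexplained death.
- Primary effectiveness 2: ischemic stroke combined with systemic embolism.
- Primary safety: a composite that ends at 7 days or discharge.
- Secondary: under SAP 1.4.3, ischemic stroke combined with systemic embolism.
- Descriptive (SAP 1.4.4): the only cerebrovascular item is TIA.

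None of the 13 does. The serious adverse event summary in SAP 3.2 gives counts and percentages of subjects, not a 24-month rate.

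**Step 3. Which event does the prediction cover?** The source is redacted. The only CHA₂DS₂-VASc rates in the documents (protocol Section 3) are annual ischemic stroke rates: 0.6% at a score of 1, 4.8% at 4, and more than 12% at 9. If those are the reference, the SAP counts an event that the prediction does not.

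**Step 4. Scale (illustration only).** The documents give no systemic embolism rate. This study's own sample size is not visible, and the figure of 1000 is pooled with other post-approval studies. The calculation below therefore uses no sample size. It is crude and ignores censoring.

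- Let *f* be the share of subjects with a SAP event whose only event is systemic embolism. Assumed range: 0–20%.
- Let *r* be observed/predicted under the protocol event. Assumed range: 0.4–0.6.
- The prediction is held fixed as a stroke-only rate (a further assumption, used in the last column).

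SAP rate ÷ protocol rate = 1/(1 − *f*).

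Loss in relative reduction = *r*/(1 − *f*) − *r* = *r f*/(1 − *f*).

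| *f* | 1/(1 − *f*) | *f*/(1 − *f*) | Loss at *r* = 0.4 to 0.6 (percentage points) |
|---|---|---|---|
| 0% | 1.00 | 0 | 0 |
| 5% | 1.05 | 0.0526 | 2.1 to 3.2 |
| 10% | 1.11 | 0.1111 | 4.4 to 6.7 |
| 20% | 1.25 | 0.25 | 10.0 to 15.0 |

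For example, with *r* = 0.4 and *f* = 10%, the reduction of 60% under the protocol event becomes 1 − 0.4 × 1.1111 = 55.6% under the SAP event, a loss of 4.4 points.

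**The case against.** The mismatch in wording cannot be disputed. What can be argued is how much follows from it.

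- **The SAP may be the matched version.** The protocol introduces the score through a paper whose title (reference 9) covers thromboembolism as well as stroke. The source of the quoted rates (reference 10) is titled for ischemic stroke. The predicted rate could rest on either. This stands, and it is why the fix has to be conditional. It is also a reason to reconcile, because the visible text does not choose.
- **The redacted sections may settle the analysis.** They could name ischemic stroke or report it separately. This stands as a limit: the statement that no endpoint isolates ischemic stroke applies to the visible text. Redacted text cannot, however, make two complete and different definitions agree.
- **The direction is conservative.** Adding systemic embolism can only leave the event count unchanged or raise it. Against a stroke-only prediction, the SAP wording would understate any reduction, so it could not make the device look better than it is. This stands and limits the severity.
- **The size is hypothetical.** Neither *f* nor *r* has a basis in the documents, the range starts at no effect, and if the prediction includes thromboembolism the losses are not a bias. This stands too.
- **The overlap with primary endpoint 2 is legitimate, and stroke data are still collected.** One event may properly be compared with both a fixed goal and a risk-score prediction. Strokes are recorded on a dedicated form (protocol Section 6), and endpoints are adjudicated (protocol Section 11). So the data are not lost. What is missing from the visible SAP is a planned 24-month rate for ischemic stroke alone.

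**Conclusion.** The concern holds. The protocol and the SAP define the secondary endpoint on different events, and nothing visible reconciles them. Under the SAP wording, no visible endpoint gives the 24-month rate of ischemic stroke alone. Confidence in the mismatch is high. The consequence for what will actually be reported depends on redacted text.

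The actual size cannot be computed. On the assumptions stated, the SAP rate would be 1.00 to 1.25 times the protocol rate. The relative reduction against a stroke-only prediction would be understated by 0 to 15.0 percentage points. The three primary endpoint tests are not affected. This should be corrected, but it does not threaten the study's main conclusions.

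**What to change.** Bring protocol 14.2 (with 4.3.2 and the Synopsis) and SAP 1.4.3 to one observed event, the same one that the predicted-rate source measures.

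- If that source gives ischemic stroke rates, as the figures in protocol Section 3 do, delete the systemic embolism phrase from SAP 1.4.3.
- If it also covers systemic embolism, amend the three protocol statements and add the 24-month rate of ischemic stroke alone to the SAP.

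The cost is one phrase in the SAP, or one phrase in three protocol places plus one extra rate from events already collected. No new data are needed.

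A minor related check concerns the score itself. Protocol Table 3 prints the two-point age category as above 75 and the one-point category as 65–74, so age 75 goes unscored. Section 3 gives two points from age 75 upward. The symbol may have been altered in PDF conversion. If it was not, the table and Section 3 need to be reconciled, which is a change to one cell.
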